Clinically important differences for primary and secondary outcomes: Because a large number of patients are affected by PPCs and undergo abdominal surgery, even small percent differences in the outcomes to be studied represent a large absolute number of patients that could be affected by the studied intervention. Accordingly, we will consider clinically significant: (a) a 10% difference in the primary outcome of the study (the row mean score test of a Cochran-Mantel-Haenszel, which incorporates both the frequency and highest grade of severity of PPCs during the first 7 days after surgery; (b) 5% difference in the rate of composite or isolated PPCs; (c) 5% difference in the rate of intraoperative and major extrapulmonary complications; (d) a difference of 12h in the length of postoperative oxygen therapy/other respiratory support; (e) a difference of half-day in the length of hospital stay.

Plasma biomarkers. We hypothesize that the PRIME-AIR bundle will minimize lung mechanical injury and inflammation by reducing overinflation and atelectasis.

Accordingly, it will reduce plasma levels of biomarkers of inflammatory, epithelial and endothelial injury. Plasma will be collected from all patients for analysis of a focused panel of plasma biomarkers of inflammation (cytokines IL-6, IL-8); epithelial injury (the soluble form of the receptor for advanced glycation end-products, RAGE, and club cell protein 16, CC16), and endothelial injury (angiopoietin-2, Ang-2). We will compare biomarker levels in the PRIME-AIR bundle vs. control groups before, at the end of and 24h after surgery. Blood collection in this aim will not only allow for the biomarkers analysis, but also for the creation of a biobank for future studies on PPCs.

Blinding: Because the intraoperative and postoperative interventions cannot be blinded, each site will have at least 2 members of the research team: one to perform the randomization, education, and implementation of the protocol in the operating room and postoperative incentive spirometry/mobilization during hospital visits (in-person or videoconference); and another, blinded to patient allocation, to assess PPCs and all other outcomes -with information obtained from the participant's medical chart and phone calls to the participant (phone script in Attachments/Insight). Investigators performing biomarker assays will also be blinded to study group.

VI. STATISTICAL ANALYSIS

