- iii. an abscess or other evidence of infection involving the deep incision is found on direct examination, during surgery, or by histopathological or radiological examination.
- iv. an abscess or other evidence of infection involving the organ/space that is found on direct examination, during reoperation or by histopathological or radiological examination.
- d. diagnosis of a surgical site infection by a surgeon or attending physician.
- Urinary tract infection: A simplified version of the CDC recommendations defines a urinary tract infection as follows: a positive urine culture of $\geq 10^5$ colony forming units per mL with no more than two species of micro-organisms, and with at least one of the following symptoms or signs: fever ($> 38^\circ\text{C}$), urgency, frequency, dysuria, suprapubic tenderness, costovertebral angle pain or tenderness with no other recognized cause⁷².
- Coagulation
 - Disseminated Intravascular Coagulation (DIC): defined following the 2001 definition by the International Society on Thrombosis and Hemostasis (ISTH): “DIC is an acquired syndrome characterized by the intravascular activation of coagulation without a specific localization and arising from different causes. It can originate from and cause damage to the microvasculature, which if sufficiently severe, can produce organ dysfunction”⁷⁴. It will be diagnosed following the modified algorithm currently used and described⁷⁵:

Acute DIC Algorithm Proposed by the International Society on Thrombosis and Haemostasis^a

Algorithm

1. Presence of an underlying disorder known to be associated with DIC?
If yes: proceed. If no: do not use this algorithm
2. Global coagulation results:
 - a. Platelet count ($> 100,000/\mu\text{L} = 0$, $< 100,000/\mu\text{L} = 1$, $< 50,000/\mu\text{L} = 2$)
 - b. Fibrin degradation products such as D-dimer (no increase = 0, moderate increase = 2, strong increase = 3)
 - c. Prolonged prothrombin time (< 3 seconds = 0, > 3 seconds = 1, > 6 seconds = 2)
 - d. Fibrinogen level ($> 1.0 \text{ g/L} = 0$; $< 1.0 \text{ g/L} = 1$)

DIC, disseminated intravascular coagulation.

^aInterpretation of algorithm: A score of 5 or higher is compatible with acute DIC. The algorithm can be repeated on occasion if acute DIC remains a consideration and the laboratory values change. Modified from Taylor et al.⁶

- Postoperative hemorrhage: defined as blood loss within 72 h after the start of surgery which would normally result in transfusion of blood.

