4.5.2 Safety Outcomes

The co-primary safety outcomes will be: 1) the proportion of patients with any intraoperative cardiovascular events or pneumothorax; and 2) the proportion with both intraoperative hypoxemia and rescue recruitment maneuvers. Specifically:

- Proportion of participants with intraoperative cardiovascular events (hypotension, bradycardia, tachycardia, arrhythmias, new ST-segment changes, and cardiac arrest) or pneumothorax
- Proportion of participants with both intraoperative hypoxemia and rescue recruitment maneuvers

Other secondary safety outcomes include:

- Length of postoperative oxygen therapy/other respiratory support
- Length of hospital stay
- Proportion of participants with any major extrapulmonary complications (detailed definition is in Appendix I of the protocol; included in Appendix 3 of this document for reference)

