Appendix 3. Details of Targeted Adverse Events

- Rate of major extrapulmonary complications, defined based on existing diagnosis in the medical chart following usual accepted definitions⁶¹ unless otherwise specified:
 - Cardiovascular:
 - myocardial ischemia or infarction: Increase in serum cardiac biomarker values (preferably cardiac troponin) with at least one value above the 99th percentile upper reference limit and at least one of the following criteria⁶⁵:
 - Symptoms of myocardial ischemia;
 - New ischemic ECG changes;
 - Development of pathological Q waves;
 - Imaging evidence of new loss of viable myocardium or new regional wall motion abnormality in a pattern consistent with an ischemic etiology;
 - Identification of a coronary thrombus by angiography or autopsy.
 - cardiogenic pulmonary edema: Cardiogenic pulmonary edema is defined as evidence of fluid accumulation in the alveoli due to poor cardiac function.
 - arrhythmia: electrocardiograph (ECG) evidence of cardiac rhythm disturbance.
 - cardiac arrest: The International Liaison Committee on Resuscitation defines cardiac arrest as the cessation of cardiac mechanical activity, as confirmed by the absence of signs of circulation⁶⁸.
 - stroke: defined as an embolic, thrombotic or hemorrhagic cerebral event with persistent residual motor, sensory or cognitive dysfunction (e.g. hemiplegia, hemiparesis, aphasia, sensory deficit, impaired memory).
 - Gastrointestinal:
 - bleeding: Gastrointestinal bleed is defined as unambiguous clinical or endoscopic evidence of blood in the gastrointestinal tract. Upper gastrointestinal bleeding (or hemorrhage) is that originating proximal to the ligament of Treitz, in practice from the esophagus, stomach and duodenum. Lower gastrointestinal bleeding is that originating from the small bowel or colon.
 - anastomotic breakdown: Leak of luminal contents from a surgical connection between two hollow viscera. The luminal contents may emerge either through the wound or at the drain site, or they may collect near the anastomosis, causing fever, abscess, septicemia, metabolic disturbance and/or multiple organ failure. The escape of luminal contents from the site of the anastomosis into an adjacent localized area, detected by imaging, in the absence of clinical symptoms and signs should be recorded as a subclinical leak⁶⁹.
 - paralytic ileus: Failure to tolerate solid food or defecate for three or more days after surgery⁷⁰.

- Liver Disease:

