Liver failure: serum bilirubin level $>34 \mu\text{mol/L}$ with elevation of the transaminase and lactic dehydrogenase levels above twice normal values.
- Acute renal failure: Stage 1 or higher Kidney Disease Improving Global Outcomes (KDIGO) guidelines⁷¹ (Table A1).

Table A1 Kidney Disease Improving Global Outcomes Guidelines (KDIGO)

Stage	Serum Creatinine	Urine Output
1	1.5–1.9 times baseline value within 7 days or $\geq 27 \text{ mmol/L} (\geq 0.3 \text{ mg/dL})$ increase within 48 h	$\leq 0.5 \text{ mL/kg/h}$ for 6–12 h
2	2.0–2.9 times baseline value within 7 days	$\leq 0.5 \text{ mL/kg/h}$ for 12 h
3	3.0 times baseline value within 7 days or Increase in serum creatinine to $\geq 354 \text{ mmol/L} (\geq 4.0 \text{ mg/dL})$ with an acute rise of $>44 \text{ mmol/L} (0.5 \text{ mg/dL})$ or Initiation of renal replacement therapy	$\leq 0.3 \text{ mL/kg/h}$ for 24 h or Anuria for 12 h

- Systemic inflammatory response syndrome (SIRS): Defined by the presence of two or more of the following⁶⁰
 - Temperature $>38^\circ\text{C}$ or $<36^\circ\text{C}$
 - Heart rate $>90/\text{min}$
 - Respiratory rate $>20/\text{min}$ or $\text{PaCO}_2 <32 \text{ mmHg} (4.3 \text{ kPa})$
 - White blood cell count $>12\,000/\text{mm}^3$ or $<4\,000/\text{mm}^3$
- Infections
 - Source uncertain: The CDC defines infection, source uncertain as one where there is strong clinical suspicion of infection but the source has not been confirmed because clinical information suggests more than one possible site, meeting two or more of the following criteria⁷² core temperature $<36^\circ\text{C}$ or $>38^\circ\text{C}$; white cell count $>12 \times 10^9/\text{L}$ or $<4 \times 10^9/\text{L}$; respiratory rate >20 breaths/minute or $\text{PaCO}_2 <4.7 \text{ kPa} (35 \text{ mmHg})$; pulse rate >90 beats/minute
 - Bacteremia (bloodstream infection): The CDC defines laboratory confirmed bloodstream infection as one which meets at least one of the following criteria⁷² which should not be related to infection at another site:
 - 1) Patient has a recognized pathogen cultured from one or more blood cultures and the organism cultured from blood is not related to an infection at another site.
 - 2) Patient has at least one of the following signs or symptoms: fever $> 38^\circ\text{C}$, chills or hypotension, and at least one of the following:

- a. Common skin contaminant cultured from two or more blood cultures drawn on separate occasions

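### The only tested composite of postoperative extrapulmonary harm weights low-threshold findings the same as stroke, cardiac arrest or sepsis, so it can mask a rise in serious complications

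*SAP*

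**What the plan says.** SAP 4.5.2 lists "Proportion of participants with any major extrapulmonary complications" among the other secondary safety outcomes, below two co-primary ones that are both intraoperative. The components are set by cross-reference: "detailed definition is in Appendix I of the protocol; included in Appendix 3 of this document for reference". No severity grade, hierarchy or overall follow-up window is attached. Under SAP 6.1.4 and 8.2 the outcome is tested with a site-stratified Cochran-Mantel-Haenszel test and reported as a relative risk with a 95% confidence interval.

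SAP Appendix 3, matching Protocol Appendix I, includes these items:

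- "Systemic inflammatory response syndrome (SIRS): Defined by the presence of two or more of the following" (temperature, heart rate, respiratory rate or PaCO2, white cell count), with no duration or treatment requirement.
- "paralytic ileus: Failure to tolerate solid food or defecate for three or more days after surgery".
- Acute renal failure at "Stage 1 or higher Kidney Disease Improving Global Outcomes (KDIGO) guidelines", where Stage 1 can be met by low urine output over 6 to 12 hours.
- Arrhythmia, meaning any rhythm disturbance on ECG, treated or not.

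The same list holds myocardial infarction, cardiac arrest, stroke, sepsis and DIC. The lead-in says complications rest on a diagnosis already in the chart, unless specified otherwise.

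Protocol section V (Exploratory Outcomes) lists the rate of each extrapulmonary complication and all-cause mortality at days 7, 30 and 90. SAP 4.5 and 8 carry neither forward.

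**The concern.** An any-event composite records only whether a patient had at least one item. A patient who has already qualified through SIRS or ileus adds nothing more if a stroke follows. The more common the low-threshold items are, the less an excess of serious events can move the composite, and the closer its relative risk lies to 1.

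One component also overlaps with the efficacy target. Pneumonia in Protocol Table 5 needs infiltrates plus two of three signs, among them fever or hypothermia and an abnormal white count. A patient with pneumonia, a temperature above 38°C and a white count above 12,000 meets two SIRS criteria and can count as an extrapulmonary event. If the bundle works on pneumonia, the composite can fall for that reason and offset real harm elsewhere.

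At stake is the main published statement on postoperative extrapulmonary safety. A relative risk near 1 would be read as reassurance whether or not serious events had risen.

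**Working it through.** **The plan's own figure.** There is none to reproduce. Neither document gives a rate, power or sample size for this composite. The 93% in SAP 4.6 belongs to the primary outcome and plays no part here.

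**Inputs.**
- n = 375 per arm (SAP 4.6) and two-sided 0.05.
- Assumed, because the documents give no rates: serious-event rate s of 10% in controls against 15% or 20% with the bundle; routine-finding rate m from 0 to 50%, equal in both arms and independent of serious events.
- The 5-point step has the size of the difference the protocol calls clinically important, a "5% difference in the rate of intraoperative and major extrapulmonary complications" (read as absolute points). That threshold is set for the composite as defined, not for a serious subset, so here it is only a convenient step.

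**Formulas.**
- Composite rate: C = 1 − (1 − s)(1 − m). The absolute difference between arms is therefore the serious-event difference times (1 − m).
- Power: Φ[(d − 1.96·SE0)/SE1], plus the very small opposite tail. Here d is the difference, SE0 = √(2p̄(1 − p̄)/n) and SE1 = √([p1(1 − p1) + p2(1 − p2)]/n). Site stratification is ignored.

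**One case in full** (s = 10% v 20%, m = 50%).
- C = 1 − 0.90 × 0.50 = 0.55, and 1 − 0.80 × 0.50 = 0.60; d = 0.05.
- p̄ = 0.575, SE0 = 0.0361, SE1 = 0.0361.
- (0.05 − 1.96 × 0.0361)/0.0361 = −0.58, which gives power of 28%.

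**Serious events 10% v 20%**

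| m | Composite | Difference (points) | RR | Power |
|---|---|---|---|---|
| 0 (serious alone) | 10.0% v 20.0% | 10.0 | 2.00 | 97% |
| 10% | 19.0% v 28.0% | 9.0 | 1.47 | 83% |
| 20% | 28.0% v 36.0% | 8.0 | 1.29 | 65% |
| 40% | 46.0% v 52.0% | 6.0 | 1.13 | 38% |
| 50% | 55.0% v 60.0% | 5.0 | 1.09 | 28% |

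**Serious events 10% v 15%**

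| m | Composite | Difference (points) | RR | Power |
|---|---|---|---|---|
| 0 (serious alone) | 10.0% v 15.0% | 5.0 | 1.50 | 54% |
| 20% | 28.0% v 32.0% | 4.0 | 1.14 | 22% |
| 40% | 46.0% v 49.0% | 3.0 | 1.07 | 13% |
| 50% | 55.0% v 57.5% | 2.5 | 1.05 | 11% |

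The last entry is 10.6% with both tails counted and 10.2% in the direction of harm alone.

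**If routine findings also fall with the bundle.** Drop the equal-background assumption and let m fall by 5 points in the bundle arm, for example through fewer pneumonia-driven SIRS events. With serious events at 10% v 15%:
- m = 20% v 15%: C = 1 − 0.90 × 0.80 = 28.0%, against 1 − 0.85 × 0.85 = 27.75%. The difference is −0.25 points.
- m = 40% v 35%: C = 1 − 0.90 × 0.60 = 46.0%, against 1 − 0.85 × 0.65 = 44.75%. The difference is −1.25 points.

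In both cases a true 5-point rise in serious events appears as a small benefit.

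**The case against.** The strongest reply is that the routine-finding rate is unknown. Protocol section IX says only that complications are frequent after major abdominal surgery. The chart-diagnosis lead-in may also keep out uncharted episodes such as a fast heart rate with a raised white count. The phrase allowing other specification leaves it unclear whether the explicit SIRS, ileus and KDIGO criteria replace the charted diagnosis or merely qualify it. This stands. A reader might infer that the composite will be dominated by routine findings and cannot show serious harm. The documents do not support that: a doubling from 10% keeps 83% power at a 10% background.

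A reader might also infer that nothing else tests postoperative harm. That is wrong. SAP 4.5.1 compares Grade 3 or 4 PPCs at POD 7, 30 and 90, and ventilatory dependence or failure. The gap is confined to extrapulmonary harm. Deaths and serious, unexpected, related events went to the DSMB (SAP 4.7.3), but that is oversight and not a reported comparison between arms.

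The outcome is secondary, and under SAP 6.6 its P-value is only a summary measure if the primary outcome is not significant. Power for 10% v 15% is just 54% even undiluted, so sample size is part of the limitation. Both points stand, but neither removes the dilution of the reported relative risk.

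Finally, the SAP describes 751 participants as already studied and two interim analyses as done. Replacing a protocol-listed outcome at that stage would be a late redefinition. This also stands, and it argues for adding an outcome and not substituting one.

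**Conclusion.** The concern holds in a limited form: the composite can mask a rise in serious extrapulmonary complications. Its definition gives low-threshold items full weight, and one of them overlaps with pneumonia. The absolute excess in serious events shrinks by the factor (1 − m). At a 20% background, power for a 10% v 20% difference falls from 97% to 65%; at 50% it falls to 28%. These figures rest on assumed rates, on independence, and on equal routine-finding rates in both arms. If the bundle also reduces routine findings, the composite can point the wrong way. How much masking occurs in this trial depends on component rates and on the chart-diagnosis rule, neither of which the documents settle. Protocol section VI makes the final SAP definitive where the two differ, so leaving component rates and mortality out of the SAP matters.

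**What to change.** Keep the protocol-listed composite as it is. Before the safety data are unblinded for the final analysis, add the following to SAP 4.5.2 and 8.2:

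- A supplementary composite that drops SIRS and ileus. Also drop kidney injury that is Stage 1 only and untreated rhythm events, if the collected data allow; the documents do not show whether treatment of rhythm events or the KDIGO stage was recorded.
- Each component, and all-cause mortality at POD 7, 30 and 90, by arm beside the composite. The protocol already lists these as exploratory outcomes.
- A sentence saying whether a charted diagnosis is required for items with explicit criteria, and the follow-up window for both composites.

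The cost is SAP text and one more derived variable. The restricted composite will have fewer events and a wider confidence interval. Because it comes after the interim analyses, it should be labelled as added in the SAP.

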4.6 Sample Size

We estimated that 40% of participants in the control group would have pulmonary complications. If the bundle decreases the proportion of participants with complications by 35.29% (i.e, 25.88% would have complications in the intervention group compared to 40% in the control group), with no change in the distribution of the severity of complications, 750 participants (375 / treatment group), will provide 93% power to

detect the treatment effect as statistically significant (Cochran-Mantel-Haenszel test, row mean score test; $\alpha=0.05$, two-sided; based on simulations). The grant proposal contained a detailed discussion of the assumptions.

When the study was fully implemented the study team realized that approximately 6% of randomized participants would fail to be included in the study (revoking assent/consent on the day of surgery; no longer being a candidate for surgery; other reasons). The study team had not anticipated that this would occur. Therefore, we revised our plan to recruit approximately 795-800 participants to achieve 750 randomized participants having surgery with written consent.

4.7 Data monitoring through study

4.7.1 Routine monitoring and quality control

The study data was subject to routine checks, initially monthly but then every two weeks. Query reports were run on the data and individual query reports were sent to sites. Separate reports were prepared for the unblinded coordinator(s) (which included screening issues) and the blinded coordinator(s). Query reports addressed incomplete or missing forms, illogical or inconsistent data, range checks for values and dates, and other issues as needed. Sites were required to address all queries on the report and return them to the SDCC data manager in a timely manner and resolve issues with the SDCC data manager as necessary.

Monthly quality monitoring reports were generated through the course of the study for the CCC. This included details about the implementation of incentive spirometry, ambulation, and about doses and monitoring of neuromuscular blocking agents and their reversal in intervention participants for each site. Data monitoring activities were unblinded, but there was no systematic summary of results, and data was used only to monitor for quality issues and track data collection.

4.7.2 DSMB monitoring

The study was monitored by a DSMB convened by NIH twice a year. The DSMB recommended continuation of the study without modification of the study protocol at each review.

4.7.3 Safety monitoring

The DSMB was notified of all deaths (within 24 hours of the SDCC becoming aware of the event). The DSMB was notified within 7 days of the SDCC becoming aware of the event of:

- all intraoperative complications judged significant by the attending anesthesiologist;

- all other adverse events occurring on the day of the surgery or the day after surgery;
- any adverse event that is serious, unexpected and suspected of being related (probably or possibly related) to the study procedures; and
- any unanticipated problems.

As specified by the central Institutional Review Board (cIRB, Massachusetts General Brigham, Boston), the cIRB was notified of all deaths and any unanticipated problems within 7 days of the SDCC becoming aware of the event and any adverse event that was serious, unexpected and suspected of being related (probably or possibly related) to the study procedures. All other adverse events were included in the annual reports to the cIRB.

4.8 Ethical Issues

The cIRB approval was obtained by the Clinical Coordinating Center (CCC), which covered all but one site (Miami Veterans Administration) that obtained its local IRB approval. A separate IRB approval was obtained by the Statistics and Data Coordinating Center (SDCC).

5 Additional Measurements Included in Primary Paper

5.1 Baseline Characteristics

The following characteristics will be used to describe the participants in the study

- age, gender (female), race (White/Black/Asian/Other or more than one race), Hispanic, BMI
- comorbidities (active cancer; hypertension; GERD; diabetes)
- medications (statin use).
- total ARISCAT score on the day of surgery
- ASA Physical status
- hemoglobin
- preoperative O₂ saturation
- primary surgical organ classified as: gastric; pancreatic; hepatobiliary [combined]; colorectal [combined]; urological (kidney, bladder combined), and other
 - more than one organ is possible
 - “other” is used for surgery addressing topography other than those specified

